10.3 POST STUDY OBSERVATION

After 24-month long term follow up, the investigator may report any changes in outcomes for patient specifically related to:

- Progression of disease or relapse
- Survival information

10.4 CLINICAL ASSESSMENTS

10.4.1 Medical History and demography

Medical history will include demographic data (e.g., date of birth, race/ethnicity) and additional relevant medical information including:

- all medical conditions and disease states that require current or ongoing therapy, and
- other medical conditions and disease states that, in the opinion of the Investigator, are relevant to the patient's study participation

10.4.2 Physical examination

The physical Examination performed in this study will include height, weight, blood pressure, pulse and body temperature and a physical (external) assessment of the patient. Blood pressure and pulse may be measured whilst the patient is sitting or lying but must be measured consistently for the patient throughout the study. Temperature should be measured in accordance with the centre's standard practice. Any significant abnormalities noted during the physical examination at screening should be reported in the Medical History. Any significant changes noted on follow up physical examination should be reported as adverse events.

10.4.3 ECOG Performance assessment

A patient's performance Status will be assessed using the Eastern Co-operative Oncology Group (ECOG) Performance Score (Appendix 1).

10.4.4 Electrocardiography

12-lead ECGs will be taken using a serviced and calibrated machine in triplicate, within 5 minutes of each other (over 15 minutes), to calculate the mean QTc value to ensure the patients eligibility for study enrollment. ECGs should be taken after the patient has been resting supine for 5 minutes.

ECG will be performed at three timepoints throughout the study – Screening, End of Treatment visit and end of study. Any abnormalities noted during the physical examination at screening should be reported in the Medical History. Any changes noted on follow up ECG on should be reported as adverse events.

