10 STUDY PROCEDURES

10.1 OUTCOME MEASURES

The outcome measures supporting the primary objective of this study are:

- Number of events of > Grade 2 toxicity (as scored by CTCv4.03)
- Number of events of > Grade 2 toxicity considered by the investigator and / or the Sponsor as causally related to the use of NOX66 (as scored by CTCv4.03)
- The overall number of adverse events considered by the investigator and / or the Sponsor as causally related to the use of NOX66
- Incidence of dose limiting toxicities (DLT) and or maximum tolerated dose (MTD) of NOX66

The outcome measures supporting the secondary objectives of this study are:

- Where target (measurable) lesions have been identified:
 - a. Change intumour size of irradiated lesions according to RECIST1.1 criteria, as assessed by central review and by the investigator based on CT/MRI scan
 - b. Change in tumour size of target non-irradiated lesions according to RECIST1.1 criteria, as assessed by central review and by the investigator based on CT/MRI scan
 - c. Observation of change from baseline in Non-target lesions according to RECIST 1.1 criteria
- For all patients – overall assessment of change in disease state by an independent Radiation Oncology Expert Committee
- Change from baseline in pain score based on responses to BPI-SF
- Observation of change from baseline in PSA levels
- Assessment of patient via physical exam and ECOG Score

- Plasma level of idronoxil post treatment (immediate and long term (at 6 weeks))
- Duration of tumour progression free state from study treatment start date
- Duration of survival from study treatment start date

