- Safety blood sampling – Complete Blood Count, Serum Chemistry and Urinalysis
- Biomarker blood sampling – PSA and idronoxil
- Administration of Brief Pain Inventory -Short Form questionnaire
- Concomitant Medication Review
- Adverse Event Review (CTCAE 4.03)
- Tumour Imaging (CT/MRI scan) and Assessment

10.2.5 Twelve-Week Follow up (Day 84 ± 7) - Visit 9

Visit 9 will occur 70 days/10 weeks post completion of NOX66 treatment and consist of the following assessments:

- Physical Examination including vital signs
- Performance Status Assessment (using ECOG performance scale)
- Electrocardiography in triplicate
- Safety blood sampling - Complete Blood Count, Serum Chemistry and Urinalysis
- Biomarker blood sampling – PSA
- Administration of Brief Pain Inventory -Short Form questionnaire¹
- Concomitant Medication Review
- Adverse Event Review (CTCAE 4.03)
- Tumour Imaging (CT/MRI scan) and Assessment

¹If pain score from assessment of response to BPI-SF questionnaire demonstrates an improvement in pain (refer to section 10.4.5) a confirmatory questionnaire at least 2 weeks later will be verbally administered to patients as described for 18-week administration of BPI-SF.

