14.1 DEFINITIONS

14.1.1 AE

AE is any un-anticipated or unintended medical occurrence or worsening of a sign or symptom (including an abnormal laboratory finding) or disease in a study participant, which does not necessarily have a causal relationship with the study condition, procedures or study agent(s) that occurs after the informed consent is obtained.

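### Section 10.4.4 makes any change on a follow-up ECG an adverse event, a wider rule than 10.4.2 or 14.1.1; this can add trivial changes to the AE tables and to one primary measure, and its ECG timepoints disagree with the visit lists

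*Combined protocol and SAP*

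**What the plan says.** Three places in the protocol bear on whether a follow-up finding becomes an AE.

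- Section 10.4.4, for ECGs: "Any changes noted on follow up ECG on should be reported as adverse events". There is no qualifier for size, clinical significance or direction.
- Section 10.4.2, for physical examination: "Any significant changes noted on follow up physical examination should be reported as adverse events".
- Section 14.1.1, the general definition: "AE is any un-anticipated or unintended medical occurrence or worsening of a sign or symptom (including an abnormal laboratory finding) or disease". This has two limbs, an occurrence or a worsening, and sets no significance threshold.

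On the schedule, 10.4.4 says "ECG will be performed at three timepoints throughout the study" and names Screening, End of Treatment and end of study. The visit list for Week 12 (10.2.5) also includes "Electrocardiography in triplicate".

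Section 10.1 lists four measures for the primary objective. Two are limited by grade: "Number of events of > Grade 2 toxicity (as scored by CTCv4.03" and "Number of events of > Grade 2 toxicity considered by the investigator and / or the Sponsor as causally related to the use of NOX66". The third is the overall number of AEs, of any grade, judged causally related to NOX66. The fourth is DLT incidence and/or MTD. The safety analysis in 12.2 also tabulates treatment-emergent AEs by dose cohort. Its other safety endpoints are laboratory results, physical examinations, vital signs and ECOG status; ECG is not named.

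**The concern.** A small rate difference or a shorter QTc is a change on the ECG, so 10.4.4 makes it an AE. It fits neither limb of 14.1.1 well, and the matching rule in 10.4.2 would leave it out. Sites in three countries (section 3.3) could therefore record the same tracing differently, depending on which section they follow.

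This matters because safety is the primary objective and the cohorts are small. In an escalation cohort of four, one patient whose only AE is an ECG record moves the cohort's AE incidence by 1/4, or 25 percentage points. Since 12.2 names no ECG endpoint, AE reporting is also the only route it specifies for ECG results to reach the tables, although ECGs are taken in triplicate and QTc is an exclusion criterion.

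**Working it through.** The plan states no figure on this point, so there is none to reproduce. The check has three parts.

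**1. Which reported results are exposed?** Consider a trivial or favourable ECG change recorded as an AE, assumed to be below Grade 2 or not gradable.

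| Result | Filter | Exposed? |
|---|---|---|
| Treatment-emergent AE tables (12.2) | none by grade or causality | yes |
| Primary measures 1 and 2 (10.1) | above Grade 2 | no |
| Primary measure 3 (10.1) | related to NOX66, any grade | only if judged related |
| Primary measure 4 (10.1) | DLT and/or MTD | not expected |
| Synopsis endpoint | toxicity of Grade 2 or more, and DLTs | no |
| Dose escalation (10.2.14) | discontinuations for NOX66-related AEs | no, unless treatment is stopped |

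For measure 3, the causality table in 14.1.3 allows a rating of possible when the timing is reasonable, even if disease or other drugs could explain the event. The End of Treatment visit falls the day after the last dose (Table 1, footnote 3), so such a rating is plausible for a change seen then. The same table also offers an unlikely/unrelated category.

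**2. How many records?** Inputs:

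- N = 24 patients (synopsis: 3 × 4 + 12), the planned maximum.
- k = follow-up ECGs per patient: 2 by 10.4.4 (End of Treatment, end of study), or 3 by the visit lists (adding Week 12).
- p = chance that a follow-up ECG shows a non-significant change. The documents do not give it; 5% to 30% is assumed.
- q = share of those records judged related to NOX66. Also not given; 10% to 50% is assumed.

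Formulas: ceiling = N × k; expected extra records = N × k × p; chance that a patient has at least one = 1 − (1 − p)^k; expected addition to primary measure 3 = N × k × p × q.

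| | k = 2 | k = 3 |
|---|---|---|
| Ceiling | 24 × 2 = 48 | 24 × 3 = 72 |
| Extra records, p = 5% | 48 × 0.05 = 2.4 | 72 × 0.05 = 3.6 |
| Extra records, p = 30% | 48 × 0.30 = 14.4 | 72 × 0.30 = 21.6 |
| Patient with at least one, p = 5% | 1 − 0.95² = 10% | 1 − 0.95³ = 14% |
| Patient with at least one, p = 30% | 1 − 0.70² = 51% | 1 − 0.70³ = 66% |
| Measure 3, lowest (p = 5%, q = 10%) | 2.4 × 0.1 = 0.2 | 3.6 × 0.1 = 0.4 |
| Measure 3, highest (p = 30%, q = 50%) | 14.4 × 0.5 = 7.2 | 21.6 × 0.5 = 10.8 |

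The ceilings assume that all 24 patients have every ECG, that every tracing differs from baseline, and that each gives one new record. The per-patient chances also treat a patient's ECGs as independent.

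**3. How many ECG timepoints?** Section 10.4.4 gives three. The visit sections give four: Screening (10.2.1), End of Treatment (Table 1 in 10.2.3), Week 12 (10.2.5) and Week 24 (10.2.7). The difference is Week 12. Section 15.3 counts an evaluation not completed as a protocol violation, so whether a missing Week 12 ECG is one depends on the section read.

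**The case against.** The strongest reply is that this is a drafting slip with little consequence. The ECG sentence is garbled, and the one before it, although in the ECG section, speaks of abnormalities found at the screening physical examination; the text looks carried over from 10.4.2 with the qualifier lost. A sensible site would read changes as new abnormalities and let 14.1.1 govern. The slip is likely, but the sentence remains an instruction to sites, and its carried-over neighbour leaves no explicit rule for recording screening ECG abnormalities, the baseline against which a change is judged.

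The objection also rightly blocks several stronger readings that a reader might infer:

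- *The rule inflates the primary safety counts in general.* It does not: only the overall count of NOX66-related AEs is open to it.
- *Sites following 14.1.1 would report almost no ECG events.* That reduces the definition to clinically significant worsening. It also admits unintended occurrences and has no significance threshold.
- *The choice of rule means 72 events against about 4.* The 72 needs the Week 12 ECG that 10.4.4 omits, and it implicitly sets the change rate at 100%. The 4 comes from an assumed 5% (72 × 0.05 = 3.6) on the other side. The contrast comes from those choices.
- *Real cardiac signals would be lost.* AEs are tabulated by system organ class, preferred term, severity and relationship (12.2), and listed per patient (synopsis). In a descriptive study of 24 patients, a serious cardiac event should remain visible.

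Finally, 12.2 leaves full analysis detail to a later SAP, so the missing ECG summary may yet be supplied. That makes it easy to add, but does not provide it.

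**Conclusion.** The inconsistency is real and its reach is limited. The reporting threshold in 10.4.4 is wider than in 10.4.2 and takes in changes that 14.1.1 would not. Inflation of the exposed results is possible but not demonstrated. Every count below the ceilings of 48 and 72 rests on an assumed change rate, and the addition to the primary measure of about 0.2 to 7 records (two follow-up ECGs) or 0.4 to 11 (three) also rests on an assumed share judged related. That the graded primary counts, the DLTs and the synopsis endpoint stay clear rests on the extra changes being low grade or ungradable. The timepoint mismatch needs no assumption. Both merit correction because the remedy is cheap.

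**What to change.** 1. In 10.4.4, limit AE reporting to a new or worsened, significant ECG abnormality relative to the screening ECG, in line with 10.4.2 and 14.1.1.
2. In the safety analysis (12.2 or the SAP to follow), add a descriptive summary of QTc change from baseline by visit and dose cohort.
3. Reconcile the ECG timepoints in 10.4.4 with the visit lists. The documents do not show which schedule is intended, and this review does not choose between them.

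The cost is one revised sentence, one added summary and one reconciled list. The QTc summary uses ECGs that are already planned and needs no extra patients. The drawback is a small reliance on the investigator's judgement of significance, which 10.4.2 already accepts for physical examination.

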10.4.6 Safety Blood Sampling

Non-fasting samples for clinical laboratory analysis will be collected as listed below:

- Complete blood count (CBC) including: white blood cells with differentials, red blood cells, haemoglobin, haematocrit, mean corpuscular volume (MCV), mean corpuscular haemoglobin (MCH), mean corpuscular haemoglobin concentration (MCHC), platelet
- Serum chemistry panel including sodium, potassium, calcium, creatinine, total protein, albumin, bilirubin (total, direct), AST/SGOT, ALT/SGPT, alkaline phosphatase (ALP)
- Urinalysis dipstick - Clarity, specific gravity, pH, protein, glucose, ketones, nitrite, leukocytes, and blood. Urine microscopy will be performed if urinalysis values are out of range and the Investigator deems that the microscopy is clinically warranted

Haematology, clinical chemistry and urinalysis will be performed by the site's local accredited laboratories.

10.4.7 Biomarker Sampling

- PSA levels will be collected at baseline, and post treatment cycle at Visit 8 (Day 43), Visit 9 (Day 84) , Visit 10 (Day 168) and Visit 11 – Visit 16 (every 3 months after Visit 10) to determine any response to treatment. PSA samples will be collected by standard practice and analysed at each site's local laboratory.
Idronoxil: Plasma samples will be collected at baseline and Visit 7 (Day 16[±]1) of treatment cycle and post treatment at Visit 8 (Day 43) to determine levels of any accumulation during and post treatment. Instructions for idronoxil plasma collection will be provided by Sponsor and analysis will be undertaken by the Sponsor performed by a designated laboratory.

10.4.8 Tumour Imaging

Tumour imaging by CT/MRI will be performed in line with local practices using a planning software system.

Baseline documentation of Target and Non-Target lesions

'Target' lesions are assessed at the designated scanning time points and defined as lesions that are measurable and:

Irradiated, such as soft tissue and lytic bony lesions, have defined margins for measurement and are irradiated at the discretion of the investigator. These lesions will be noted as 'irradiated measurable target'.

- Non-irradiated and these lesions will be noted as 'non-irradiated measurable target'.

For measurable lesions, the Longest Diameter (LD) of each lesion will be measured and a sum of the LD will be calculated and reported as the baseline sum LD. The sum LD will be used as reference by which to characterize the objective tumour response based on RECIST v1.1 criteria (see below).

Patients will undergo baseline CT or MRI body scan. A maximum of 5 lesions in total, with no more than 2 lesions per organ, will be identified as target lesions.

'Non-Target' lesions include all other lesions and are recorded at baseline as either measurable or non-measurable. For non-measurable lesions, the presence or absence of each will be noted throughout follow-up scanning time points. For measurable lesions, size (mm) will be noted throughout follow-up scanning time points.

These can include irradiated lesions such as sclerotic bone lesions, which do not have defined margins for measurements and are irradiated at the discretion of the investigator. These lesions will be assessed for local response based on patient reported outcome using the BPI-SF (see section 10.4.5).

Review of all CT/MRI scans per patient will be conducted by the independent Radiation Oncology Expert Committee as outlined in Section 10.4.9.

RECIST evaluation of target lesions

Assessment of irradiated measurable lesions will be conducted according to the RECIST1.1 Criteria for response on the CT or MRI scan, as set out below.

Complete Response (CR):	Disappearance of all relevant target lesions
Partial Response (PR):	At least a 30% decrease in the sum of the LD of relevant target lesions, taking as reference the baseline sum LD
Stable Disease (SD):	Neither sufficient shrinkage to qualify for PR nor sufficient increase to qualify for PD, taking as reference the smallest sum LD since the treatment started
Progressive Disease (PD):	At least a 20% increase in the sum of the LD of relevant target lesions, taking as reference the smallest sum LD recorded since the treatment started or the appearance of one or more new lesions.

Evaluation of non-target lesions

Non-measurable Assessment:

Complete Response (CR):	Disappearance of all non-target lesions and normalization of tumour marker level
--------------------------------	--

Non-CR/Non-PD:	Persistence of one or more non-target lesion(s) or/and maintenance of tumour marker level above the normal limits
Progressive Disease (PD):	Appearance of one or more new lesions and/or unequivocal progression of existing non-target lesions.

Measurable Assessment:

Response	Percent change in lesion size based on sum LD (mm) taking as reference the baseline sum LD.
-----------------	---

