4 INTRODUCTION

The mainstays of oncology therapy – chemotherapy and radiation therapy – provide varying degrees of efficacy in patients with cancer, and for those with late stage metastatic disease the prognosis for patients can be very poor. A primary reason for these poor outcomes is the presence of chemo- and radio-resistance mechanisms in tumour cells.¹ This resistance leads to higher doses of chemotherapy and/or radiation therapy being required, to a point where the adverse effects (toxicity) of therapy outweighing the benefits, or that treatment no longer provides any benefit for patients. Finding a treatment that can overcome some or all of these resistance mechanisms may lead to:

- Providing therapy with clinically meaningful outcomes for patients with end stage and late stage cancers
- Improving clinical outcomes for patients undergoing established chemotherapy and radiation therapy treatment
- Allowing lower doses of chemotherapy and radiation therapy to be used in future treatment of patients, providing similar efficacy outcomes while minimizing toxicity – providing treatment for patients who may otherwise not receive treatment (e.g. frail and elderly patients)

This study will investigate the use of NOX66 - idronoxil formulated in a lipophilic base – in combination with palliative radiation therapy, in patients with end stage castrate resistant prostate cancer. The data generated, in conjunction with other early phase studies, will be used to inform the development of larger studies to investigate the efficacy and safety of NOX66 (idronoxil) in combination with radiation therapy and chemotherapy.

The key hypotheses to be tested in this study are:

- a. That idronoxil can be safely added to palliative dose radiation therapy.
- b. That idronoxil, via its selective inhibition of PI3K/Akt signalling in tumour cells, may sensitise tumours to palliative doses of radiation therapy, with efficacy signals being seen in this study.
- c. That any efficacy seen in irradiated tumours may lead to an effect on non-irradiated tumours.

Furthermore, this study will investigate three doses of NOX66 to determine if there is any difference in safety and / or efficacy signals with increasing dose and to determine the optimal dose for future radiation therapy combination studies.

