6.2 SECONDARY OBJECTIVES

- To investigate whether idronoxil administered as the NOX66 formulation will sensitise end stage prostate cancer to palliative radiation therapy and provide a clinically relevant response to treatment according to:
 - RECISTv1.1 criteria for measurable lesions, within irradiated and non-irradiated target lesions
 - Improvement in total pain scores using BPI-SF instrument
 - To observe changes in serum PSA
 - Review of CT/MRI scans by Radiation Oncology Expert Committee –assessment of observable and or symptomatic changes from baseline over time
- To determine a dose of NOX66 to continue into late phase clinical trials
- To investigate plasma idronoxil levels following NOX66 therapy
- To determine Progression Free Survival (PFS) and Overall Survival (OS)

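### The progression rule applied to irradiated lesions counts new lesions anywhere in the body, with no field limit or precedence rule, so in-field responses may be recorded as PD

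*Combined protocol and SAP*

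**What the plan says.** Protocol Section 10.4.8 introduces its target-lesion response table with "Assessment of irradiated measurable lesions will be conducted according to the RECIST1.1 Criteria for response on the CT or MRI scan, as set out below". The rows then read as follows.

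- PR: "At least a 30% decrease in the sum of the LD of relevant target lesions, taking as reference the baseline sum LD". CR is limited to relevant target lesions in the same way. Neither row requires that new lesions be absent.
- PD, size limb: "At least a 20% increase in the sum of the LD of relevant target lesions".
- PD, remainder of the row: "taking as reference the smallest sum LD recorded since the treatment started or the appearance of one or more new lesions". The new-lesion limb carries no restriction by site or radiation field.

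The aims are set by lesion group. Section 6.2 asks for response by "RECISTv1.1 criteria for measurable lesions, within irradiated and non-irradiated target lesions". Section 4 separates local sensitisation, hypothesis (b), from hypothesis (c): "That any efficacy seen in irradiated tumours may lead to an effect on non-irradiated tumours". Section 10.1 lists as an outcome "Change intumour size of irradiated lesions according to RECIST1.1 criteria, as assessed by central review and by the investigator based on CT/MRI scan", with a parallel item for non-irradiated targets.

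The results are used in three places. Section 12.2 plans to report RECIST response for target and non-target lesions. Sections 10.2.14 and 13.2 bring Week 6 response data into the choice of expansion dose. Section 12.1 credits NOX66 with tumour shrinkage beyond the less-than-30% reduction expected from radiation alone.

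**The concern.** Whether irradiated lesions responded is a question about those lesions. A new lesion elsewhere is an event of the patient. The PD row puts the second into the category used for the first, so an in-field responder can carry a PD label because of something outside the field.

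The situation is plausible in this population. Section 8.2 requires progression at entry, and one route includes two or more new bone lesions.

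Two things are at stake. One is the categorical RECIST result for irradiated lesions, where the PR threshold of 30% is also the size of reduction that Section 12.1 treats as the NOX66 signal. The other is the Week 6 review. Planned escalation cohorts have four patients, so one reclassified responder moves a cohort's proportion by 1/4 = 25 percentage points if all four are assessable.

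**Working it through.** The plan states no figure for this point: no in-field response rate, no new-lesion rate and no power. There is nothing to reproduce, so the check is to apply the table literally and then show the size under stated assumptions.

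**Step 1: one patient (lesion sizes assumed).** An irradiated target goes from 50 to 30 mm, a non-irradiated target stays at 30 mm, and one new lesion appears outside the field.

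- Irradiated sum LD: (30 - 50)/50 = -40%. The PR row is met.
- New lesion present. The PD row is also met.
- Section 10.4.8 does not say which category prevails.
- All targets pooled: (60 - 80)/80 = -25%. PR is not met.

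The last line matters because Section 10.4.8 describes a single baseline sum LD and does not define *relevant*. Whether this patient meets PR by size at all depends on which sum is used.

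**Step 2: recorded response rate.** Let R be the true in-field CR/PR rate and q the share of in-field responders with a new lesion. Assume that PD prevails and that new lesions are independent of local response. Then recorded rate = R × (1 - q). The documents give neither R nor q.

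- R = 40%, q = 20%: 0.40 × 0.80 = 32%.
- R = 40%, q = 40%: 0.40 × 0.60 = 24%.

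The loss is 8 to 16 points.

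**Step 3: expected counts over a wider range.** Expected responders recorded as PD = N × R × q. The chance of at least one is 1 - (1 - R × q)^N.

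| N with a measurable irradiated target | R | q | Expected true responders | Expected recorded as PD | Chance of at least one |
|---|---|---|---|---|---|
| 24 | 20% | 10% | 4.8 | 0.48 | 0.38 |
| 24 | 20% | 25% | 4.8 | 1.2 | 0.71 |
| 24 | 20% | 50% | 4.8 | 2.4 | 0.92 |
| 24 | 40% | 10% | 9.6 | 0.96 | 0.63 |
| 24 | 40% | 25% | 9.6 | 2.4 | 0.92 |
| 24 | 40% | 50% | 9.6 | 4.8 | 0.995 |
| 12 | 20% | 10% | 2.4 | 0.24 | 0.22 |
| 12 | 20% | 25% | 2.4 | 0.6 | 0.46 |
| 12 | 20% | 50% | 2.4 | 1.2 | 0.72 |

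N = 24 is the planned maximum (3 × 4 + 12) and supposes that every patient has a measurable irradiated target. N = 12 is an assumed lower case, since Section 10.4.8 expects some irradiated lesions, such as sclerotic bone, to be non-measurable.

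**The case against.** The strongest reply is that the in-field evidence survives. Section 10.1 lists size change separately for irradiated and non-irradiated targets. Section 10.4.8 measures each target's diameter and labels it by irradiation status. Section 12.1 attributes effect by size reduction, not by response category. Section 7 gives local response its own review by the investigator with the ROEC, and non-measurable irradiated lesions are judged by pain score. The synopsis promises per-patient listings and no formal statistical analysis. The expansion dose is a committee judgement on several inputs, not a formula. Section 12.2 leaves full detail to a later SAP, and Section 10.4.9 leaves ROEC documentation to sponsor guidelines, so a derivation rule could sit in either.

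Most of this stands, and it rules out several stronger readings that a reader might infer.

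- *In-field responders will be recorded as local failures.* PD overriding PR is the likely reading but is not a stated rule, and the documents do not speak of local failure.
- *The radio-sensitisation question is answered with the wrong classification.* It does not rest on this category alone.
- *Hypotheses (b) and (c) cannot be separated.* They can, from the collected diameters. That the same new lesion also makes the non-irradiated set PD is an inference: Section 9.3 has both kinds of target assessed by RECIST 1.1, but the sentence introducing the table names irradiated lesions only.

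The reply does not remove the defect. The Section 10.1 outcomes are themselves to be judged by RECIST 1.1 criteria, which Section 10.4.8 sets out in this table. They are judged by both central review and the investigator, who could resolve the PR/PD overlap differently. The local-response review in Section 7 has no criteria. Nothing in the protocol says that a separate in-field sum will be calculated.

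**Conclusion.** The point holds as a defect in the classification rule. Followed as written, the table lets an out-of-field event label the irradiated set PD, against the Section 6.2 aim of response within each lesion group. This can understate in-field response in the categorical RECIST output and at the Week 6 dose-expansion review. It does not destroy information.

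Only patients with all three of a measurable irradiated target, an in-field response and a new lesion are affected, and the documents do not allow that number to be estimated. The fall from 40% to 24-32%, and the range of about 0.5 to 4.8 patients out of 24, illustrate assumed rates with independence and PD prevailing; they are not forecasts. Independence is itself open to doubt, because hypothesis (c) supposes that in-field efficacy may affect disease elsewhere. The result is descriptive and secondary, but the correction is specific and cheap enough to be worth making.

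**What to change.** In Section 10.4.8, and in the SAP:

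1. Define two sums, one for irradiated and one for non-irradiated measurable targets, each with its own baseline and smallest value, and replace the undefined *relevant* with a reference to these.
2. Classify each set as CR, PR, SD or PD by change in its own sum LD only, with PD by the 20% rule.
3. Record new lesions as a separate item. They already count as PD in the non-target assessment, so no progression event is lost.
4. Add a short patient-level overall-response definition, and apply the new-lesion criterion only there and to PFS.
5. List percent change in the two sums side by side for each patient, including at the Week 6 review.

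The cost is wording in the protocol, SAP and scan form, plus one added overall-response table. No new scans or readers are needed.
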